10.9.5. Population PK/PD Dataset File Structure : Oxygen Saturation/PASP

The PME compliant file structure is a space-delimited file with each row containing the following columns of information. Data from all treatments will be included.

Decision as to whether this will be required will be made following the planned interim analysis (for study Part 2 at approximately N=3 or approximately N=6).

Variable short name	Assessment description	Format	Unit	Valid Values / Format
C	Data Identifier	Integer	-	0
STUD	Protocol Number	Integer	-	204987
DRUG	Name of Drug	Integer	-	Maximum 10 characters (numeric or text). 2586881
SUBJ	Subject identifier in study	Integer	-	Maximum 10 characters (numeric or text). Different identifier for each subject
CENT	Study centre identifier	Integer	-	
LABL	Indicator field describing the type of assessment in that record	Integer	See footnotes	See footnotes
AMT	Dose of GSK2586881	Decimal	Mg	Amount of drug given = Total GSK2586881 dose (mg/kg) * WT. AMT=0 when LABL=0 For dosing events: total dose of GSK2586881 taken For concentration events: 0
INF	Infusion Time	Decimal	h	Time during which total dose infused. (Time at end of infusion – Time of start infusion)
RATE	Rate of Infusion	Decimal	Mg/h	Rate of infusion (AMT/INF)

Variable short name	Assessment description	Format	Unit	Valid Values / Format
DGRP	Treatment Identifier	Decimal	-	DGRP=0 for placebo treatment treatment DGRP=0.8 for 0.8 mg/kg treatment Dose of GSK2586881 (for all events)
PART	Study Part	Integer	-	1=Part 1 or 2=Part 2
PERIOD	Study Period	Integer	-	1=Period 1 or 2=Period 2
DAY	Study day	Integer	-	Maximum 10 characters (numeric or text) N= Day N, Actual Study Day
CTIM	Clock time of Dose or measurement	HH:MM:SS	-	
DATE	Date of record	DD/MM/YYYY		
TRFD	Actual time relative to FIRST dose	Decimal	Hours	When LABL=1 or 4, TIME =0 Hours since start of FIRST infusion (on Day 1). For pre-dose sample, TRFD is relative to FIRST dose
TRLD	Actual time relative to LAST dose	Decimal	Hours	When LABL=0 or 4, TIME=0 Hours since start of LAST dose/infusion. For pre-dose sample, TRLD is relative to previous dose For single dose studies TRLD = TRFD
TFLAG	Time Flag	Integer	-	At T0 and LABL=6, TFLAG=0 At T1 and LABL=6, TFLAG=1 At T2 and LABL=6, TFLAG=2 At T3 and LABL=6, TFLAG=3 At T4 and LABL=6, TFLAG=4 Otherwise if LABL=6, TFLAG=5 If LABL="0" or "4", TFLAG=6
BLPASP	PASP	Decimal	mmHg	Baseline Value
PASP	PASP	Decimal	mmHg	When LABL=6, PASP at time specified by TRLD. When LABL=1, or 4, PASP=0
BLOS	Oxygen Saturation	Decimal	%	Baseline Value
OS	Oxygen Saturation	Decimal	%	When LABL=6, Oxygen Saturation at time specified by TRLD. When LABL=1 or 4, Oxygen Saturation=0
EVID	Event Identification data item	Integer	-	Flag indicating whether LABL contains dosing admin info or drug concentration data. Valid values are - 1 – each dosing record for subject 0 - for all other records

Assessments captured in the LABL variable

Label	Description	Units
0	Dosing record for placebo	
4	Dosing records for 0.8 mg/Kg GSK2586881	
6	Observed record (concentration or ratio) at time specified by TRLD; excludes NA, IS and NR	

10.10. Appendix 10: Abbreviations & Trade Marks

10.10.1. Abbreviations

Abbreviation	Description
ACE2	Angiotensin converting enzyme type 2
ADaM	Analysis Data Model
AE	Adverse Event
AIC	Akaike's Information Criteria
ALT	Alanine aminotransferase (SGPT)
Ang II	Angiotensin II
AST	Aspartate aminotransferase (SGOT)
AUC(0-2.5h)	Area under the concentration-time curve over the study period
AUC(0.5-2.0h)	Area under the concentration-time curve over the hypoxia challenge
A&R	Analysis and Reporting
BUN	Blood urea nitrogen
CDISC	Clinical Data Interchange Standards Consortium
CI	Confidence Interval
CL	Clearance
Cmax	Maximum observed plasma concentration
CO2	Carbon Dioxide
CPMS	Clinical Pharmacology Modelling & Simulation
CS	Clinical Statistics
CSR	Clinical Study Report
CTR	Clinical Trial Register
CV _b / CV _w	Coefficient of Variation (Between) / Coefficient of Variation (Within)
DOB	Date of Birth
DP	Decimal Places
ECG	Electrocardiogram
eCRF	Electronic Case Record Form
GSK	GlaxoSmithKline
GUI	Guidance
HPV	Hypoxic Pulmonary Vasoconstriction
IA	Interim Analysis
ICH	International Conference on Harmonisation
IDMC	Independent Data Monitoring Committee
IDSL	Integrated Data Standards Library
IMMS	International Modules Management System
IP	Investigational Product
mITT	Modified Intent-To-Treat
IV	Intravenous
LOC	Last Observation Carries Forward
MMRM	Mixed Model Repeated Measures
O2	Oxygen
PASP	Pulmonary Artery Systolic Pressure

Abbreviation	Description
PCI	Potential Clinical Importance
PD	Pharmacodynamic
PDMP	Protocol Deviation Management Plan
PK	Pharmacokinetic
PP	Per Protocol
PVR	Pulmonary Vascular Resistance
QC	Quality Control
QTcF	Fridericia's QT Interval Corrected for Heart Rate
QTcB	Bazett's QT Interval Corrected for Heart Rate
RAP	Reporting & Analysis Plan
RAMOS	Randomization & Medication Ordering System
RAS	Renin-Angiotensin System
SAC	Statistical Analysis Complete
SDTM	Study Data Tabulation Model
SOP	Standard Operation Procedure
TA	Therapeutic Area
TFL	Tables, Figures & Listings
Tmax	Time to maximum observed concentration
T1/2	Apparent terminal phase half-life
V	Volume of Distribution
VO2	Oxygen Consumption

10.10.2. Trademarks

Trademarks of the GlaxoSmithKline Group of Companies	Trademarks not owned by the GlaxoSmithKline Group of Companies
HARP	R (Statistical programming package/language)
RANDALL NG	SAS
	WinNonLin

10.11. Appendix 11: List of Data Displays

10.11.1. Data Display Numbering

The following numbering will be applied for RAP generated displays:

Section	Tables	Figures
Study Population	1.1 to 1.n	1.1 to 1.n
Efficacy	2.1 to 2.n	2.1 to 2.n
Safety	3.1 to 3.n	3.1 to 3.n
Pharmacokinetic	4.1 to 4.n	4.1 to 4.n
Pharmacodynamic and / or Biomarker	5.1 to 5.n	5.1 to 5.n
Pharmacokinetic / Pharmacodynamic	6.1 to 6.n	6.1 to 6.n
Section	Listings	
ICH Listings	1 to x	
Other Listings	y to z	

10.11.2. Mock Example Shell Referencing

Non IDSL specifications will be referenced as indicated and if required an example mock-up displays provided in [Appendix 12: Example Mock Shells for Data Displays](#).

Section	Figure	Table	Listing
Study Population	POP_Fn	POP_Tn	POP_Ln
Efficacy	EFF_Fn	EFF_Tn	EFF_Ln
Safety	SAFE_Fn	SAFE_Tn	SAFE_Ln
Pharmacokinetic	PK_Fn	PK_Tn	PK_Ln
Pharmacodynamic and / or Biomarker	PD_Fn	PD_Tn	PD_Ln
Pharmacokinetic / Pharmacodynamic	PKPD_Fn	PKPD_Tn	PK/PD_Ln

NOTES:

- Non-Standard displays are indicated in the 'IDSL / TST ID / Example Shell' or 'Programming Notes' column as '[Non-Standard] + Reference.'

10.11.3. Deliverable [Priority]

Delivery	Description
IA[1]	Interim Analysis (Planned to be completed by GSK) – Study Part 1
IA[2], IA[3]	Interim Analyses (Planned to be completed by GSK) – Study Part 2
SAC*	Final Statistical Analysis Complete (Planned to be completed by FSP)

***Please note that where IA and SAC are noted together next to an output, GSK internal stats and programming team will take responsibility for this output, unless otherwise stated.**

10.11.4. Study Population Tables

Study Population Tables					
No.	Population	IDSL / TST ID / Example Shell	Title	Programming Notes	Deliverable
Subject Disposition					
1.1.	miTT	ES1A	Summary of Subject Disposition for the Subject Conclusion Record		SAC
1.2.	All Subjects Screened	ES6	Summary of Screening Status and Reasons for Screen Failure		SAC
Protocol Deviation					
1.3.	miTT	DV1	Summary of Important Protocol Deviations		SAC
Populations Analysed					
1.4.	All Subjects Screened	SP1A	Summary of Study Populations	Include All Screened, miTT, miTT1, miTT2, PK1 and PK2 populations. Footnote that percentages based on those in the miTT population, so miTT1, miTT2, PK1 and PK2 pops will have a percentage.	SAC
Demographic and Baseline Characteristics					
1.5.	miTT1	DM3	Summary of Demographic Characteristics (Part 1)	Age groupings <18, 18-40 and >40 to be used. Due to study entry criteria, only 18-40 will be displayed. Only total column needs to be included for a crossover study.	SAC
1.6.	miTT2	DM3	Summary of Demographic Characteristics (Part 2)	As above (Part 2 population)	SAC
1.7.	miTT1	DM5	Summary of Race and Racial Combinations (Part 1)	Only total column needs to be included for a crossover study.	SAC

Study Population Tables					
No.	Population	IDSL / TST ID / Example Shell	Title	Programming Notes	Deliverable
1.8.	miTT2	DM5	Summary of Race and Racial Combinations (Part 2)		As above (Part 2 population)
Medical Conditions					
1.9.	miTT	MH1	Summary of Past Medical Conditions	Total column only. To be kept as overall miTT.	SAC
1.10.	miTT	MH1	Summary of Current Medical Conditions	Total column only. To be kept as overall miTT.	SAC

10.11.5. Safety Tables

Safety : Tables					
No.	Population	IDSL / TST ID / Example Shell	Title	Programming Notes	Deliverable [Priority]
PASP					
3.1.	miTT1	PFT1	Summary of PASP (Part 1)	IDSL example PFT1 can be followed ('Day' won't be needed). If a log-transformation is required for analysis please include log-transformed summary as a second page using PFT2 example.	IA[1], SAC (GSK)
3.2.	miTT2	PFT1	Summary of PASP (Part 2)	As above (Part 2 population)	SAC (GSK)
3.3.	miTT1	PFT3	Summary of PASP Change from Baseline (Part 1)	IDSL example PFT3 can be followed ('Day' won't be needed). If a log-transformation is required for analysis please include log-transformed summary as a second page using PFT2 example.	IA[1], SAC (GSK)

Safety : Tables					
No.	Population	IDSL / TST ID / Example Shell	Title	Programming Notes	Deliverable [Priority]
3.4.	miTT2	PFT3	Summary of PASP Change from Baseline (Part 2)	As above (Part 2 population)	SAC (GSK)
3.5.	miTT1	SAFE_T1 (non-standard)	Summary of Repeated Measures Bayesian Statistical Analysis of Change from Baseline in PASP (Part 1)	As per non-standard example SAFE_T1 but parameter column could be removed. Note that adjusted treatment differences and posterior probabilities (<0, <-2.5, <-5) are included on page 2 of mock example. Please note details regarding treatment differences in Section 7.2 and update output accordingly if a log-transformation is required (SAFE_T2 applies in this case with addition of posterior probabilities to be added).	IA[1], SAC (GSK)
3.6.	miTT2	SAFE_T1 (non-standard)	Summary of Repeated Measures Bayesian Statistical Analysis of Change from Baseline in PASP (Part 2)	As above (Part 2 population)	SAC (GSK)
Oxygen Saturation					
3.7.	miTT1	PFT1	Summary of Oxygen Saturation (Part 1)	IDSL example PFT1 can be followed ('Day' won't be needed). If a log-transformation is required for analysis please include log-transformed summary as a second page using PFT2 example.	IA[1], SAC (GSK)
3.8.	miTT2	PFT1	Summary of Oxygen Saturation (Part 2)	As above (Part 2 population)	SAC (GSK)
3.9.	miTT1	PFT3	Summary of Oxygen Saturation Change from Baseline (Part 1)	IDSL example PFT1 can be followed ('Day' won't be needed). If a log-transformation is required for analysis please include log-transformed summary as a second page using PFT2 example.	IA[1], SAC (GSK)

Safety : Tables					
No.	Population	IDSL / TST ID / Example Shell	Title	Programming Notes	Deliverable [Priority]
3.10.	miTT2	PFT3	Summary of Oxygen Saturation Change from Baseline (Part 2)	As above (Part 2 population)	SAC (GSK)
3.11.	miTT1	SAFE_T1 (non-standard)	Summary of Repeated Measures Bayesian Statistical Analysis of Change from Baseline in Oxygen Saturation (Part 1)	As per SAFE_T1 but parameter column could be removed. Note that adjusted treatment differences are included on page 2 of mock example. For OS expecting that we'll need to update the Posterior Probability labels, to <0%, <-3%, <-5%, where 5% is the clinical concern level for a treatment difference where GSK reduces OS to a greater extent. Please see Section 8.1.2 with regards to changes required should a log transformation be needed (SAFE_T2 applies in this case with addition of posterior probabilities to be added).	IA[1], SAC (GSK)
3.12.	miTT2	SAFE_T1 (non-standard)	Summary of Repeated Measures Bayesian Statistical Analysis of Change from Baseline in Oxygen Saturation (Part 2)	As above (Part 2 population)	SAC (GSK)
Pulmonary Vascular Resistance (PVR)					
3.13.	miTT2	PFT1	Summary of Pulmonary Vascular Resistance (PVR) (Part 2)	See comments for PASP	SAC (GSK)
3.14.	miTT2	PFT3	Summary of Pulmonary Vascular Resistance Change from Baseline (PVR) (Part 2)	See comments for PASP	SAC (GSK)
3.15.	miTT2	SAFE_T1 (non-standard)	Summary of Repeated Measures Bayesian Statistical Analysis of Change from Baseline in Pulmonary Vascular Resistance (PVR) (Part 2)	See comments for PASP. Note that adjusted treatment differences and posterior probabilities would initially be (<0, <0.1, <0.3)	SAC (GSK)

Safety : Tables					
No.	Population	IDSL / TST ID / Example Shell	Title	Programming Notes	Deliverable [Priority]
Adverse Events (AEs)					
3.16.	mITT1	AE1CP (same as CP_AE1x)	Summary of All Adverse Events by System Organ Class and Preferred Term (Part 1)	Summarise by treatment group. Any pre-treatment AEs to be included in the listing only. Will only be created for interim if sufficient number of AEs are observed.	IA[1] (GSK), SAC (FSP)
3.17.	mITT2	AE1CP (same as CP_AE1x)	Summary of All Adverse Events by System Organ Class and Preferred Term (Part 2)	As above (Part 2 population)	SAC (FSP)
3.18.	mITT1	AE1CP (same as CP_AE1x)	Summary All Drug-Related Adverse Events by System Organ Class and Preferred Term (Part 1)	Summarise by treatment group.	SAC
3.19.	mITT2	AE1CP (same as CP_AE1x)	Summary All Drug-Related Adverse Events by System Organ Class and Preferred Term (Part 2)	As above (Part 2 population)	SAC
3.20.	mITT1	AE1CP (same as CP_AE1x)	Summary of All Serious Adverse Events by System Organ Class and Preferred Term (Part 1)	Production of this will be dependent on the number of SAEs, listing may suffice (based on clin pharm IDSL standards advice, this is a conditional summary). Summarise by treatment group. Any pre-treatment SAEs to be included only in listing.	SAC
3.21.	mITT2	AE1CP (same as CP_AE1x)	Summary of All Serious Adverse Events by System Organ Class and Preferred Term (Part 2)	As above (Part 2 population)	SAC
ECG					
3.22.	mITT1	EG1	Summary of ECG Findings (Part 1)		SAC
3.23.	mITT2	EG1	Summary of ECG Findings (Part 2)		SAC
3.24.	mITT1	EG2	Summary of ECG Values (Part 1)		SAC
3.25.	mITT2	EG2	Summary of ECG Values (Part 2)		SAC
3.26.	mITT1	CP_EG11	Frequency of ECG Values by Pre-Specified PCI Categories (Part 1)	Categories as per PCI details in Section 10.6.2.	SAC

Safety : Tables					
No.	Population	IDSL / TST ID / Example Shell	Title	Programming Notes	Deliverable [Priority]
3.27.	miTT2	CP_EG11	Frequency of ECG Values by Pre-Specified PCI Categories (Part 2)	As above (Part 2 population)	SAC
3.28.	miTT1	EG2	Summary of Change from Baseline in ECG Values (Part 1)		SAC
3.29.	miTT2	EG2	Summary of Change from Baseline in ECG Values (Part 2)		SAC
3.30.	miTT1	CP_EG12	Frequency of Change from Baseline ECG Values by Pre-Specified PCI Categories (Part 1)	Categories as per PCI details in Section 10.6.2.	SAC
3.31.	miTT2	CP_EG12	Frequency of Change from Baseline ECG Values by Pre-Specified PCI Categories (Part 2)	As above (Part 2 population)	SAC
Vital Signs					
3.32.	miTT1	VS1	Summary of Vital Signs (Part 1)		SAC
3.33.	miTT2	VS1	Summary of Vital Signs (Part 2)		SAC
3.34.	miTT1	VS1	Summary of Change from Baseline in Vital Signs (Part 1)		SAC
3.35.	miTT2	VS1	Summary of Change from Baseline in Vital Signs (Part 2)		SAC
Immunogenicity					
3.36.	miTT	IMM1	Summary of Positive Immunogenicity Results	Can be kept as miTT overall	SAC

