
 Refer to Section 7.2. PVR will be analysed in the same manner as for the primary endpoint PASP. Posterior probabilities of interest to include (looking for high probabilities to favour increases to a lesser extent in PVR on GSK2586881): 
 Probability that change from baseline in PVR is reduced by GSK2586881 (i.e., probability that a treatment difference is negative, or if a log transformation is applied then the probability that the ratio is less than 1). Probability that change from baseline in PVR is reduced by >=0.1 wood units and >=0.3 wood units (i.e., probability that a treatment difference is <=-0.1 wood units and <=-0.3 wood units. In the case of a log-transformation, ratios of interest would be <0.95 and 0.90, representing 5% and 10% difference between groups) Probability cut-offs may be re-assessed at the time of analysis
Model Checking

 Refer to: Appendix 8: Model Checking and Diagnostics for Statistical Analyses
Model Results Presentation (Part 2 only)

 Summary tables for absolute and change from baseline by treatment and timepoint (T0 to T4) Listing of absolute data Individual subject profiles by treatment group and timepoint

Planned Statistical Analyses

- Summary table of statistical analysis, adjusted change from baseline posterior medians and 95% credible intervals by treatment and timepoint, together with estimated posterior median treatment differences (GSK2586881 – Placebo) and 95% credible intervals for the change from baseline at times T1 to T4 along with posterior probabilities of interest
- Figure of absolute PVR by timepoint
- Figure of statistical analysis adjusted change from baseline medians and 95% credible intervals by treatment group and timepoint

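### The Table 3.15 note drops the minus signs from the PVR probability cut-offs, so two columns would not measure the reductions defined in Section 8.1.2

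*SAP*

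**What the plan says.** Section 8.1.2 of the SAP sets out the PVR analysis. In words, the quantity is "Probability that change from baseline in PVR is reduced by >=0.1 wood units and >=0.3 wood units". In symbols, it is "probability that a treatment difference is <=-0.1 wood units and <=-0.3 wood units". The reported contrast is "estimated posterior median treatment differences (GSK2586881 – Placebo"), so a benefit is negative. The section looks for high probabilities "to favour increases to a lesser extent in PVR on GSK2586881".

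The display list in Section 10.11.5 then tells the programmer what to put in Table 3.15: "Note that adjusted treatment differences and posterior probabilities would initially be (<0, <0.1, <0.3"). The first cut-off agrees with Section 8.1.2. The second and third have the right size but no minus sign.

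The parallel notes in the same list keep their signs. For PASP (Table 3.5) the note has "posterior probabilities (<0, <-2.5, <-5) are included on page 2 of mock example". For oxygen saturation (Table 3.11) it asks the programmer to "update the Posterior Probability labels, to <0%, <-3%, <-5"%.

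**The concern.** Section 8.1.2 and the Table 3.15 note describe the same two columns and cannot both be followed. Section 8.1.2 asks how probable it is that the drug lowers PVR, relative to placebo, by at least a stated amount. The note as written asks how probable it is that the drug does not raise PVR by more than that amount. The second question is much easier to answer favourably, and it gets easier as the cut-off grows.

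At stake is how the PVR table is read. Under the rule in Section 8.1.2 that high values favour the drug, the two columns could look encouraging when there is no effect, or when PVR is higher on active treatment.

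**Working it through.** **1. Could the missing signs be a text-extraction loss?** Unlikely. The minus signs survive in the notes for Tables 3.5 and 3.11 in the same list, and in the PVR text of Section 8.1.2.

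**2. Does another reading reconcile the two places?** If the numbers are signed differences, <0.1 and <0.3 include increases in PVR. If they are sizes of reduction, <0 would mean an increase and <0.1 a reduction smaller than 0.1, which is the opposite of Section 8.1.2. No single convention makes all three cut-offs match.

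**3. Ordering, with no assumption.** Let D be the active-minus-placebo difference. For any posterior:

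- Table 3.15 as written: P(D<0) ≤ P(D<0.1) ≤ P(D<0.3)
- Section 8.1.2: P(D<0) ≥ P(D≤-0.1) ≥ P(D≤-0.3)

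The column meant to be the most demanding can therefore never be lower than the column for any reduction.

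**4. Size, under an assumption.** The SAP gives no posterior SD for PVR. I take D as normal with mean m and SD s, with s assumed to lie between 0.1 and 0.5 Wood units. Then P(D<c) = Φ((c − m)/s).

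Worked case, no effect, m = 0 and s = 0.3:

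- As written: Φ(0.1/0.3) = 0.631 and Φ(0.3/0.3) = 0.841
- As defined in Section 8.1.2: Φ(−0.1/0.3) = 0.369 and Φ(−0.3/0.3) = 0.159

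Worked case, PVR higher on active, m = +0.1 and s = 0.2:

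- As written: Φ((0.1 − 0.1)/0.2) = Φ(0) = 0.500 and Φ((0.3 − 0.1)/0.2) = Φ(1) = 0.841
- As defined in Section 8.1.2: Φ((−0.1 − 0.1)/0.2) = Φ(−1) = 0.159 and Φ((−0.3 − 0.1)/0.2) = Φ(−2) = 0.023

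Over the assumed range:

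| m | s | P(D<0) | As written: <0.1 / <0.3 | Section 8.1.2: <=-0.1 / <=-0.3 |
|---|---|---|---|---|
| 0 | 0.1 | 0.500 | 0.841 / 0.999 | 0.159 / 0.001 |
| 0 | 0.2 | 0.500 | 0.691 / 0.933 | 0.309 / 0.067 |
| 0 | 0.3 | 0.500 | 0.631 / 0.841 | 0.369 / 0.159 |
| 0 | 0.5 | 0.500 | 0.579 / 0.726 | 0.421 / 0.274 |
| +0.1 | 0.1 | 0.159 | 0.500 / 0.977 | 0.023 / 0.000 |
| +0.1 | 0.2 | 0.309 | 0.500 / 0.841 | 0.159 / 0.023 |
| +0.1 | 0.3 | 0.369 | 0.500 / 0.748 | 0.252 / 0.091 |
| +0.1 | 0.5 | 0.421 | 0.500 / 0.655 | 0.345 / 0.212 |

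The choice between < and <= has no effect for a continuous posterior. Only the sign matters.

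**The case against.** The strongest reply is that this is a typing slip in a display note and that the governing analysis text is right, in words and in symbols. The note also refers back to the PASP comments, whose cut-offs are negative, and the mock shell SAFE_T1 has negative columns, so an attentive programmer could recover the intention. If the table were built literally, a column headed <0.3 would be numerically true. The same page would show the posterior median, its credible interval and the correct probability of any reduction, and the values rising from left to right would themselves be a warning. PVR is exploratory with Part 2 displays only. The success rule uses PASP and oxygen saturation, and PVR is not among the planned Part 2 interim outputs. Finally, the note calls its values initial, Section 8.1.2 says "Probability cut-offs may be re-assessed at the time of analysis", and a log transformation would replace the Wood-unit cut-offs with ratios.

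Most of this stands as a limit on the consequences. It does not make the instruction right. The pointer to the PASP row leads to cut-offs in mmHg, and SAFE_T1 carries those same PASP values, so the Table 3.15 note is the only place in the display list that gives PVR cut-offs. Unlike the oxygen saturation note, it does not itself cite Section 8.1.2. Freedom to revise the cut-offs later does not explain two conflicting starting values, and no positive cut-off for the PVR difference is described anywhere else.

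**Conclusion.** The concern holds. The Table 3.15 note contradicts Section 8.1.2. Followed literally, it yields two columns that do not measure a reduction in PVR and that run in the wrong order. The reversed order holds for any posterior. The size depends on the assumed normal posterior and SD: at no effect, the <0.3 column would show between 0.726 and 0.999 where the intended probability lies between 0.274 and 0.001. The reach is limited to two columns of one exploratory Part 2 table. The model, the data, the column for any reduction and the study's success rule are unaffected. It should be corrected before the table is programmed.

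**What to change.** In Section 10.11.5, change the Table 3.15 note so that the cut-offs read <0, <=-0.1 and <=-0.3 Wood units, and add a reference to Section 8.1.2 so that the definition and the display stay tied together. The cost is one line in the display specification, with no change to data collection, the model or study conduct.

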10.11.6. Safety Figures

Safety : Figures					
No.	Population	IDSL / TST ID / Example Shell	Title	Programming Notes	Deliverable [Priority]
PASP					
3.1.	mITT1	(non-standard)	Summary of PASP (Absolute) (Part 1)	x-axis will be timepoints T0 to T4, see other mock examples, y-axis will be mean PASP including 95% CI, by treatment groups (add to legend). If data is log-transformed for the analysis then this graphic will need to show geometric means and 95% CIs.	IA1, SAC (GSK)
3.2.	mITT2	(non-standard)	Summary of PASP (Absolute) (Part 2)	As above (Part 2 population)	SAC (GSK)
3.3.	mITT1	SAFE_F1 (non-standard)	Adjusted Median Responses and 95% Credible Interval vs Time Profiles of Change from Baseline in PASP (Part 1)	If possible please also add a horizontal line within the graph to indicate the 'hypoxia' in chamber period (approx 30 mins post dose to 120 mins post-dose). Add major tick marks for labels indicated in example graphic. Major tick marks to be PTM labels (or shortened version of). If data is log-transformed for analysis then this graphic will be presenting median ratios.	IA[1], SAC (GSK)
3.4.	mITT2	SAFE_F1 (non-standard)	Adjusted Median Responses and 95% Credible Interval vs Time Profiles of Change from Baseline in PASP (Part 2)	As above (Part 2 population)	SAC (GSK)

Safety : Figures					
No.	Population	IDSL / TST ID / Example Shell	Title	Programming Notes	Deliverable [Priority]
3.5.	miTT1	SAFE_F2 (non-standard)	Individual Subject Profiles of PASP (Part 1)	Adjust as space permits, with fewer subjects per page if needed. X-axis and footnote for illustration, can be amended/improved. Vertical reference lines represent start and stop of hypoxia/chamber period.	IA[1], SAC (GSK)
3.6.	miTT2	SAFE_F2 (non-standard)	Individual Subject Profiles of PASP (Part 2)	As above (Part 2 population)	IA[2], IA[3], SAC (GSK)
Oxygen Saturation					
3.7.	miTT1	(non-standard)	Summary of Oxygen Saturation (Absolute) (Part 1)	x-axis will be timepoints T0 to T4, see other mock examples, y-axis will be mean Oxygen Saturation including 95% CI, by treatment groups (add to legend) If data is log-transformed for the analysis then this graphic will need to show geometric means and 95% CIs.	IA[1], SAC (GSK)
3.8.	miTT2	(non-standard)	Summary of Oxygen Saturation (Absolute) (Part 2)	As above (Part 2 population)	SAC (GSK)
3.9.	miTT1	SAFE_F1 (non-standard)	Adjusted Median Responses and 95% Credible Interval vs Time Profiles of Change from Baseline in Oxygen Saturation (Part 1)	As above for PASP figure	IA[1], SAC (GSK)
3.10.	miTT2	SAFE_F1 (non-standard)	Adjusted Median Responses and 95% Credible Interval vs Time Profiles of Change from Baseline in Oxygen Saturation (Part 2)	As above (Part 2 population)	SAC (GSK)
3.11.	miTT1	SAFE_F2 (non-standard)	Individual Subject Profiles of Oxygen Saturation (Part 1)	As above for PASP figure	IA[1], SAC (GSK)

Safety : Figures					
No.	Population	IDSL / TST ID / Example Shell	Title	Programming Notes	Deliverable [Priority]
3.12.	miTT2	SAFE_F2 (non-standard)	Individual Subject Profiles of Oxygen Saturation (Part 2)	As above (Part 2 population)	IA[2], IA[3], SAC (GSK)
3.13.	miTT2	PD_F1 (non-standard)	Scatter Plot of Oxygen Saturation vs PASP (Part 2)	miTT2 population only Scatter plot: PASP on y axis, treatment groups side by side, timepoint (T0 to T4) split into panels.	SAC
Pulmonary Vascular Resistance (PVR)					
3.14.	miTT2	(non-standard)	Summary of Pulmonary Vascular Resistance (Absolute) (Part 2)	x-axis will be timepoints T0 to T4, see other mock examples, y-axis will be mean PVR including 95% CI, by treatment groups (add to legend) If data is log-transformed for the analysis then this graphic will need to show geometric means and 95% CIs.	SAC (GSK)
3.15.	miTT2	SAFE_F1 (non-standard)	Adjusted Median Responses and 95% Credible Interval vs Time Profiles of Change from Baseline in Pulmonary Vascular Resistance (Part 2)	See PASP comments	SAC (GSK)
3.16.	miTT2	SAFE_F2 (non-standard)	Individual Subject Profiles of Pulmonary Vascular Resistance (PVR) (Part 2)	See PASP comments	SAC (GSK)

